c. The waveform data will be synchronized and subject to data analysis at a later time, looking specifically at waveform changes in response to fluid resuscitation types, rates and volumes, response to fluid therapy, types of injuries, operative timing and management, length of ICU and hospital stay, as well as survival. These results will be compared to existing LBNP waveform data. LBNP is a laboratory model of human hemorrhage that redistributes intravascular volume to the pelvis and lower extremities, thereby inducing central hypovolemia

D. Data Analysis

[figure not shown]
- All analyses will be conducted using SAS for Windows vs. 9.3 (SAS Institute Inc., Cary NC, USA) on de-identified data. Outcome and effect variables that are not normally distributed will be either categorized or analyzed using non-parametric methods. Missing data will be managed during analysis using the method proposed by [name] et al.⁴
- 2. Randomization effectiveness: Effectiveness of randomization will be examined by comparing the two groups regarding demographic variables (age, gender), injury severity (Injury Severity Score, blunt versus penetrating mechanism), degree of shock (Field SBP, Field Heart rate, Field Hematocrit), and a field coagulation measure (Field INR). We will adjust all analyses of endpoints for the covariates showing different distribution (either statistically significant difference at p<0.05 or clinically significant difference as determined by the DSMB). Specifically, adjustment for these pre-specified, potential confounders will be performed using three different methods according to the type of endpoint:

 - a. Categorical variables: we will use multiple logistic regression (polytomous logistic regression will be used for non-binary variables);
 - b. Continuous normally distributed endpoints: we will utilize mixed linear models to adjust for confounders, assuming an unstructured covariance structure.
 - c. Continuous non-normally distributed endpoints: if the endpoint is nonnormally distributed, we will attempt first to transform the variable to approximate normality (e.g., log transformation), and if this fails, we will resort to categorization based on previously determined, clinically relevant cutoffs.⁷⁹⁻⁸³

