Boundaries will be used to declare a statistically significant difference between the two groups at an earlier stage without inflating the overall experiment errors. These interim analyses will be conducted by [name] and [name] using SAS vs. 9.3 data and reported to the DSMB, both in table format and in user-friendly graphs illustrating the test score, rejection and acceptance regions, as in the example below:

At each interim stage, if the test statistic falls into a rejection zone, the null hypothesis may be rejected and the DSMB will use this as one of the criteria for recommending early interruption of the trial. Otherwise, the trial continues to the next stage. At the final stage, the null hypothesis is rejected if Z falls into a rejection region. Otherwise, the null hypothesis is not rejected. In the example illustrated in the figure, the test statistic does not fall into the rejection regions for looks 1 and 2, and so the trial continued to the final analysis 3 when the test statistic fell into the rejection region, and the null hypothesis was rejected.

The results of the interim analyses described above will be just one of the criteria used by the DSMB to recommend early interruption of the trial as explained in more detailed later in this document.

- 6. Covariates for analysis: Please see description of randomization effectiveness for more details. (Section IV.D.2) In brief, potential covariates include: demographic variables (age, gender), injury severity (Injury Severity Score, blunt versus penetrating mechanism), degree of shock (Field SBP, Field Heart rate, Field Hematocrit), and a field coagulation measure (Field INR). We will adjust the analyses of endpoints only for the above-mentioned covariates showing different distribution (either statistically significant difference at p<0.05 or clinically significant difference as determined by the DSMB).

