- d. **Statistical test:** these outcomes are often skewed and non-normally distributed. Log transformation has been shown to be a good alternative to approximate normality for them. Thus, we will utilize linear regression to examine differences between the two groups. If adjustment for covariates is needed, we will proceed with the method for continuous normally distributed variables. In the case, normality cannot be achieved (as determined by the Shapiro-Wilk test for

^{†††} Although the hypothesis is worded as longer, the tests will be two-tailed to examine association in either direction.

normality), and there is no need to adjust for confounders, we will report median and interquartile ranges as measures of data central tendency and dispersion and use the Wilcoxon test to evaluate differences. If adjustment for covariates is needed, then we will resort to categorization of the outcomes, based on previously established, clinically meaningful cutoffs.⁸⁰ Overall experiment error will be adjusted for the number of adverse-outcomes-free-days parameters being analyzed using the Bonferroni method.

4. Temporal trends:

a. Coagulation Profile: We will assess temporal trends from pre-hospital coagulation variables (as described below) at 2, 4, 6, 12, 24, 72 hours and 28 days post-injury. The proposed coagulation measurements will also test the efficacy of plasma first resuscitation, since plasma is primarily employed for restoring levels of Factors II, V, VII, X and possibly XIII with a goal of greater than 20%, which is known to be effective for the cessation of surgical bleeding¹⁰⁷. In addition, there are major changes in the post-shock plasma affecting levels of proteins involved in regulating proteolysis, membrane lipid binding and stabilizing potentially cytotoxic intracellular components released after tissue injury.

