Mixed linear modeling with SAS Proc Mixed allows for incomplete data, thus all observed points will be used in the analysis. Missing data in temporal trends will be dealt with differently depending on the reason for missing. If MAR (loss to followup, withdrawn from study), multiple imputation methods will be used, as recommended by the Panel on Handling Missing Data in Clinical Trials. However, as described in previous sections, a major reason for missing data in these cases is early death, resulting in data MNAR, for which we will use the same approach to deal with the missing data as described for the secondary endpoints.

A similar analysis will be carried out for temporal trends in Proteomic Profile, Actin and Neutrophil Elastase inhibitors.

5. Blood components transfusion in the first 12 hours postinjury

a. Packed Red Blood Cells (RBC) volume

1. **Hypothesis:** The volume of RBC transfused in the first 12 hours postinjury will be larger among control patients compared to the experimental group patients.

b. Plasma volume

- **1. Hypothesis:** The volume of plasma transfused in the first 12 hours postinjury will be larger among control patients compared to the experimental group patients.
- 2. Statistical test for a.1 and b.2: These variables are usually non-normally distributed, thus the Wilcoxon non-parametric test will be used to compare the two groups and median/interquartile range will be used to express data central tendency and dispersion. If adjustment for covariates is needed, we will follow the procedure described for continuous, not normally distributed variables. Overall experiment error will be adjusted for the number of blood transfusion parameters being analyzed using the Bonferroni method.
- c. **Time to first RBC:** This is a variable of high importance for DOD, which leads to direct application in war theater trauma.

- **1. Hypothesis:** Time to the first RBC will be longer among patients in the experimental group compared to control patients.

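### Adjusted analyses of outcome-free days and 12-hour transfusion volumes fall back on categorisation, which loses power that an ordinal model on the uncut value would keep

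*Combined protocol and SAP*

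**What the plan says.** Section IV.D.1 gives the general rule: "Outcome and effect variables that are not normally distributed will be either categorized or analyzed using non-parametric methods". Section IV.D.2 then sets out how endpoints are adjusted when a baseline covariate is unbalanced, meaning "either statistically significant difference at p<0.05 or clinically significant difference as determined by the DSMB". Under item c, a non-normal continuous endpoint is first transformed; if that fails, "we will resort to categorization based on previously determined, clinically relevant cutoffs". Item a, on categorical endpoints, adds that "polytomous logistic regression will be used for non-binary variables", so more than two categories are possible.

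Two exploratory sections apply this rule:

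- **IV.G.3, adverse-outcome-free days.** If normality cannot be reached (judged by Shapiro-Wilk) and no adjustment is needed, the Wilcoxon test is used. Otherwise: "If adjustment for covariates is needed, then we will resort to categorization of the outcomes, based on previously established, clinically meaningful cutoffs".
- **IV.G.5, RBC and plasma volume in the first 12 hours.** The Wilcoxon test is the planned analysis. However: "If adjustment for covariates is needed, we will follow the procedure described for continuous, not normally distributed variables".

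No cutoffs are printed for either group of outcomes; the text only cites references. No adjusted rank-based or ordinal method is named. For admission INR, TEG G, base deficit and lactate, section IV.F instead names the method for normally distributed variables if adjustment is needed.

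**The concern.** A chance imbalance in one covariate changes the analysis of these outcomes from a rank test on the full scale to a comparison of categories. That changes both the power and the quantity compared, for a reason unrelated to the outcome. The cutoffs are not written down, and the loss depends strongly on where they fall.

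The consequence is limited but real. Section IV.I.1 concedes low power for the primary and some secondary endpoints, and makes statistically significant exploratory results one of the criteria for calling the therapy promising enough for Phase 3. Power lost on transfusion volume or outcome-free days therefore bears on a stated decision.

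**Working it through.** **1. The plan's own continuous figure.** The documents give no information-loss figure, so the starting point is a continuous power statement. The November 2016 addendum for admission INR has a difference of 0.19, SD 0.5 and 112 per arm. The standardised drift is 0.19 / (0.5 × √(2/112)) = 2.84. The fixed-design power is Φ(2.84 − 1.96) = 0.81, and integrating over the five printed O'Brien-Fleming boundaries gives 0.802, against 0.80 stated. The initial TEG G table (60 per arm, difference 1.18, SD 2.3, three looks) gives 0.797. The plan's framework reproduces.

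**2. How often adjustment is triggered.** The listed covariates are age, gender, Injury Severity Score, mechanism, field SBP, field heart rate, field hematocrit and field INR. If independent, the chance of at least one p<0.05 is 1 − 0.95⁸ = 0.34. Correlation would change this, and DSMB judgement adds to it.

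**3. Whether transformation can succeed.** The addendum in IV.E reports that 55% of group A and 61% of group B required transfusion, so 45% and 39% did not. A log transform cannot remove a spike of that size at zero in RBC volume. Ventilator-free days are set to 0 for death or for 28 or more ventilated days, and cannot exceed 28. IV.G.5 itself calls the transfusion volumes usually non-normal.

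**4. Loss from a two-way split.** With a fraction p above the cut and a normal shift, the information kept relative to the t-test is φ(c)² / [p(1 − p)]. The protocol's printed cutoffs serve only as examples of plausible cut positions:

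| Source of p | p | φ(c) | Kept | Lost |
|---|---|---|---|---|
| TEG G>5, mean 4.90, SD 2.30 | 0.483 | 0.399 | 0.636 | 36% |
| INR>1.5, initial table | 0.36 | 0.374 | 0.607 | 39% |
| INR>1.5, initial table | 0.28 | 0.337 | 0.562 | 44% |
| INR>1.5, initial table | 0.24 | 0.311 | 0.530 | 47% |
| INR>1.5, addendum | 0.18 | 0.262 | 0.466 | 53% |

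Against the Wilcoxon test, multiply the information kept by π/3: the loss runs from 33% to 51%. Under a logistic shape the loss is 1 − 3p(1 − p), from 25% to 56%.

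**5. Loss with more categories.** For k ordered categories under a normal shift, the information kept is Σ(Δφ)²/P. Three categories lose 19% to 21%; four lose 12% to 14%.

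**6. If the polytomous model is unordered.** A test with 80% power has noncentrality (1.960 + 0.842)² = 7.85. Three categories keep 7.85 × 0.793 to 7.85 × 0.810 = 6.23 to 6.36; tested on 2 df, power is 0.60 to 0.61. Four keep 7.85 × 0.861 to 7.85 × 0.883, about 6.75 to 6.93; on 3 df, power is 0.57 to 0.58. Using the order would give 0.70 to 0.71 and 0.74 to 0.75. A median split gives 0.61.

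**7. A zero-inflated illustration.** The assumptions are mine: 42% zeros in controls, proportional odds with odds ratio 2, 112 per arm, two-sided 5%. Simulated power is 0.79 for the Wilcoxon test, 0.74 for none versus any, about 0.28 when only the top 10% or so of controls lie above the cut, and 0.62 for four unordered categories.

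**The case against.** The strongest case against the point is about reach. A reader might infer that the fallback threatens the continuous secondary endpoints. The documents do not support that: for adjusted INR, TEG G, base deficit and lactate, section IV.F names the normal-theory method. The primary endpoint and the death-or-MOF composite are binary. The two places that clearly invoke categorisation are both exploratory. This stands and limits the point.

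A reader might also infer that any skewed variable, such as lactate, would suffer. It would not if the skew is roughly lognormal: the log transform then works, and the plan would use a linear model on the log scale without reaching the fallback.

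Nor should a loss of a third to a half be read as general. Polytomous regression is allowed, and three or four ordered categories lose much less. The 36% to 53% benchmark assumes a normal shift, whereas the rule applies only to non-normal data. Both qualifications stand. The polytomous rescue is only partial, because the plan does not say that the ordering is used.

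The route is also conditional on non-normality, a failed transformation and a covariate imbalance. For transfusion volume and outcome-free days the first two are close to given, and the third is roughly a one-in-three event on the p-value rule alone.

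Finally, clinical cutoffs do have value: they give readable risks and, when fixed beforehand, limit data-driven choice. That supports reporting them, but here no cutoffs are printed for these outcomes.

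**Conclusion.** The point holds as a minor one. When adjustment is triggered, outcome-free days and 12-hour transfusion volumes will very likely be categorised, with a loss of power that has no statistical need. The loss is about a third to a half of the information for a two-way split near cutoffs like those printed elsewhere in the protocol, and about 12% to 21% for three or four ordered categories. With an unordered polytomous model, power is close to that of a median split.

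The sizes rest on a normal-shift benchmark and on one illustrative zero-inflated setting with an assumed odds ratio and zero share. The 34% trigger assumes independent covariates. The simulation compared unadjusted tests; the gain from the adjusted ordinal model was not itself simulated.

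One inconsistency needs settling. IV.D.2.c is written for any non-normal continuous endpoint, while IV.F assigns four continuous secondary endpoints to the normal-theory method. For INR the question is live: a normal variable with mean 1.32 and SD 0.5 would have 1 − Φ((1.50 − 1.32)/0.5) = 36% above 1.5, against 18% stated in the addendum. The documents do not say which rule prevails, so the effect on those endpoints cannot be asserted.

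**What to change.** In IV.D.2.c, IV.G.3 and IV.G.5, replace the categorisation fallback with proportional-odds regression on the uncategorised value, using the same covariates. With treatment as the only term, its score test is the Wilcoxon test, so the adjusted analysis extends the planned unadjusted one. Keep cutoffs for description and for the separately stated binary hypotheses (INR>1.5, TEG G>5.0).

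State in IV.D.2 or IV.F which rule governs adjusted INR, TEG G, base deficit and lactate if they prove non-normal.

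The cost is a wording change, with no new data. The downsides are small: reliance on a proportional-odds assumption, and an odds ratio that is less direct than a difference in risk or mean. Medians or category percentages can be reported beside it.

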- **3. Intent to treat analysis:** primary and secondary outcome data will be collected in all patients regardless of treatment received.⁸⁴ An "intent-to-treat" approach will be used for all primary/secondary outcome analyses, i.e., we will compare the outcomes of the two groups according to the group assignment at time of randomization, regardless of what treatment participants actually received. Phase 2 trial, this approach will allow a preliminary evaluation of the

effectiveness of the proposed treatment (in addition to the efficacy assessment), since the health care of the subjects reflects the health care available to civilian trauma. More details are given in the sections describing statistical analysis as well as the missing data prevention and treatment.⁸⁴

In addition to the "intent to treat" approach, this study design also supports that exploratory analyses assess the association between the dose of plasma received in the field and the primary/secondary outcomes, an equivalent to the estimand "Outcome Improvement in Tolerators" described by the Panel on Handling Missing Data in Clinical Trials.⁸⁴ This will provide information on possible "dose-response" patterns for Phase 3 trials.

- 4. Power analysis: Power analyses for each primary endpoint in Stage I and II were performed using Pass 11 (Hintze, J. (2011). PASS 11. NCSS, LLC. Kaysville, Utah, USA. www.ncss.com). All power analyses account for two interim analyses for a total of three sequential, equally spaced analyses, assuming attrition rates of 0%, 10%, and 20%.
- 5. Interim analyses: We planned 5 analyses (4 interim, 1 final), equally spaced, using the O'Brien-Fleming method to calculate two-sided boundaries, assuming a 95% confidence and 80% power. Spacing will be defined by number of enrolled patients. The first look at the data will be done when one third of the predicted total enrollment has been reached and all patients accrued have been observed for the total 28-day period or till death, whatever occurs earlier. The first interim analysis will be conducted when n=50, the second at n=100, the third at n=150, the fourth at n=200 and the final at end of the 5-year period of accrual.

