There are several explanations for the differences in the expected and observed values. First, for the most common injury mechanisms, the case-fatality rate is decreasing in our trauma center ([name] et al. JAMA, 2016). Second, the wide use of TEG-guided hemostatic resuscitation in our institution has been associated with a dramatic decrease in post-injury mortality (Gonzalez, Ann Surg, 2016). In addition, our findings are not isolated. A recent multicenter RCT (Connelly et al., JAMA Surgery, 2016) also noted that the patients enrolled were less severely injured than anticipated based on previous experiences. Given the time required to establish such intense trials, usually one to two years, the assumptions used in the calculation of the sample size can understandably become outdated. This has prompted proposals of alternative designs for RCTs, such as adaptive and Bayesian RCTs as recently described by an NIH-funded workshop (Coffey et al. Clinical trials, 2012).

Based on the explanations above, we propose a continuation of the trial to increase sample size and make it adequate to detect differences in the proposed outcomes (mortality, admission acidosis and coagulation, hemorrhage as well as requirement for blood products), as follows:

Hypothesis for primary endpoint above: 28-day mortality will be significantly higher in control patients compared to experimental patients.

With 80% power, 95% confidence and assuming 12% mortality rate in the control group (based on the second interim analyses data), with 5 interim analyses (4 interim and 1 final, of which 3 already occurred), we will require 112 patients in each group (assuming the attrition rate observed in this RCT of 12%) to detect a difference of 10 percent points. This results in a total of 224 patients, which corresponds to an increase of 74 patients over the current sample size of 150 patients. See below the significance level for the 5 analyses.

Spending = O'Brien-Fleming, N1 = 112, N2 =112, P1 = 0.12, P2 = 0.02, Continuity Correction.

		Lower	Upper	Nominal	Inc	Total	Inc	Total
Look	Time	Bndry	Bndry	Alpha	Alpha	Alpha	Power	Power
1	0.20	-4.87688	4.87688	0.000	0.000	0.000	0.00015	0.000
2	0.40	-3.35695	3.35695	0.001	0.001	0.001	0.05885	0.059
3	0.60	-2.68026	2.68026	0.007	0.007	0.008	0.25750	0.317
4	0.80	-2.28979	2.28979	0.022	0.017	0.024	0.28890	0.605
5	1.00	-2.03100	2.03100	0.042	0.026	0.050	0.19460	0.800

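### The interim schedule (n=50, 100, 150, 200 and an unnumbered final look) does not match the printed five-look boundaries, which fit only a final n of 250

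*Combined protocol and SAP*

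**What the plan says.** Section IV.D.5 (Interim analyses) states: "We planned 5 analyses (4 interim, 1 final), equally spaced, using the O'Brien-Fleming method to calculate two-sided boundaries". The metric is explicit: "Spacing will be defined by number of enrolled patients". The same paragraph then gives three statements about timing:

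- First look by fraction: "The first look at the data will be done when one third of the predicted total enrollment has been reached".
- Interim looks by count: "The first interim analysis will be conducted when n=50, the second at n=100, the third at n=150, the fourth at n=200".
- Final look by calendar: "the final at end of the 5-year period of accrual".

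Section IV.D.4 (Power analysis) still describes power calculations "for a total of three sequential, equally spaced analyses".

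The addendum of November 16, 2016, within the primary endpoint section (IV.E), revises the target: "This results in a total of 224 patients, which corresponds to an increase of 74 patients over the current sample size of 150 patients". Its table of O'Brien-Fleming spending boundaries has a time column of 0.20, 0.40, 0.60, 0.80 and 1.00, with boundaries ±4.87688, ±3.35695, ±2.68026, ±2.28979 and ±2.03100. Nowhere do the documents say that boundaries will be recomputed at the fractions actually reached.

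**The concern.** Boundaries from a spending function belong to the information fractions at which they were computed. If the looks fall elsewhere, the same Z values spend a different total alpha. With 224 patients, looks at 50, 100, 150 and 200 leave gaps of 50, 50, 50, 50 and 24, so they are not equally spaced. With a calendar ending, the last gap is unknown.

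Section IV.D.5 uses these boundaries to reject the null hypothesis at the final analysis, and as one input to the DSMB's advice on stopping at an interim. It also says they avoid inflating the overall error. As written, that assurance cannot be checked, because the final n is not tied to the boundary table and the boundaries used at the looks already taken are not stated.

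**Working it through.** **Inputs.** Looks at 50, 100, 150 and 200, and spacing by number enrolled (IV.D.5). Total 224, and the five-look boundaries (addendum, IV.E). Three-look boundaries 3.71030, 2.51142 and 1.99302 for the earlier plan, whose largest total was 150 (IV.E power tables).

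**Method.** O'Brien-Fleming-type spending with 0.025 per side. Cumulative two-sided alpha at fraction t is 4[1 − Φ(2.2414/√t)], where 2.2414 is the 0.9875 normal quantile. Boundaries are solved by recursive numerical integration for a normal Z statistic.

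**Step 1: reproduce the plan's figures.** At t = 0.2, 0.4, 0.6, 0.8 and 1.0 the method gives 4.877, 3.357, 2.680, 2.290 and 2.031, as printed. At thirds it gives 3.710, 2.511 and 1.993, also as printed. The sponsor's spending function is therefore identified.

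**Step 2: where the printed fractions put the looks.** 224 × (0.2, 0.4, 0.6, 0.8, 1.0) = about 45, 90, 134, 179 and 224. Conversely, 50/0.2 = 100/0.4 = 150/0.6 = 200/0.8 = 250, so the table fits the listed looks only with a final n of 250.

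**Step 3: fractions at 224.** 50/224 = 0.223, 100/224 = 0.446, 150/224 = 0.670, 200/224 = 0.893, then 1.

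**Step 4: boundaries at those fractions, if every look follows the spending function.**

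| n | Printed Z | Z at n/224 | Nominal p, printed | Nominal p at n/224 |
|---|---|---|---|---|
| 50 | 4.877 | 4.602 | 0.000001 | 0.000004 |
| 100 | 3.357 | 3.158 | 0.0008 | 0.0016 |
| 150 | 2.680 | 2.518 | 0.0074 | 0.0118 |
| 200 | 2.290 | 2.150 | 0.0220 | 0.0315 |
| 224 | 2.031 | 2.065 | 0.0423 | 0.0389 |

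**Step 5: overall alpha with the printed boundaries at 50, 100, 150, 200 and a final n.** The documents fix no final n for the last look, so the range below is assumed.

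| Final n | Overall two-sided alpha |
|---|---|
| 201 | 0.0436 |
| 224 | 0.0470 |
| 250 | 0.0500 |
| 275 | 0.0521 |
| 300 | 0.0536 |

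At 224, under the drift that gives 80% power in the printed design, power is 0.797 with the printed boundaries and 0.798 with the recomputed ones.

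**Step 6: looks already taken.** Assume that looks 1 and 2 used the printed three-look boundaries, 3.710 and 2.511. They spend 0.01210. The spending function allows 4[1 − Φ(2.2414/√0.670)] = 0.01232 by n = 150, so almost nothing is left for look 3. The remaining boundaries become about 3.32 (n=150), 2.20 (n=200) and 2.09 (n=224). If the printed five-look values were used from look 3 onward instead, overall alpha at 224 would be 0.0528.

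**Step 7: the leftover phrases.** One third of 150 is 50, so the first-look phrase agrees with the earlier total. One third of 224 is about 75, which does not agree with n=50. The three-analysis sentence in IV.D.4 describes the earlier three-look power tables, which are still printed.

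**The case against.** The strongest reply is that little follows in practice. At 224 enrolled the printed boundaries are slightly conservative overall and power hardly moves. That stands. A reader might infer that the plan inflates the type I error, but at the stated total it does not, unless the three-look boundaries were used at the first two looks. Otherwise it takes accrual beyond about 250.

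A reader might also infer from step 4 that a Z between 2.52 and 2.68 at n=150 would get the wrong decision. The documents do not support this, for three reasons.

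- The 2.52 assumes that looks 1 and 2 followed five-look spending on 224. Under the three-look assumption the threshold at n=150 is about 3.32, on the other side of the printed 2.68. Which boundaries were used is not stated.
- The addendum says that three of the five analyses had already occurred, so the n=150 look may be past. The same addendum reports results only from the second, so this is unclear.
- A crossing at an interim is one criterion among several for the DSMB and does not dictate the decision.

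Naming a spending function does permit recomputation at actual fractions, and the documents never say that the printed Z values apply whatever the timing. Against this, the addendum presents the table as giving the significance levels for the five analyses and does not mention recomputation. A clarifying sentence is therefore needed.

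If 224 meant evaluable patients, enrolment would be 224/0.88, or about 255, and alpha 0.0504. But the addendum gives 224 as the total with 12% attrition already included, and as 74 above 150.

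The one-third phrase and the IV.D.4 sentence are remnants of the earlier plan. They affect no remaining look, though they do confuse the current text.

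**Conclusion.** The schedule and the boundary table disagree, and the final n is not fixed. The size is modest: overall alpha is about 4.7% at 224 if the printed five-look boundaries are used throughout, and 4.4% to 5.4% for an assumed final n from 201 to 300. It is about 5.3% at 224 if looks 1 and 2 used the three-look boundaries.

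The final boundary is the clearest discrepancy. The printed 2.031 (p 0.042) is slightly more lenient than the spending function gives: 2.065 (p 0.039) if all looks follow it at 224, or about 2.09 (p 0.037) after two three-look boundaries. This compares boundaries under the spending function. It does not contradict the 4.7% total, because the printed interim values underspend at the listed looks.

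No single correct value for n=150 can be asserted. All figures treat the number enrolled as the information measure, as IV.D.5 does, and use a normal Z statistic.

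**What to change.** In IV.D.5, and where the five-look wording recurs under the endpoints:

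- Fix the final analysis at 224 enrolled, each followed to day 28 or death, in place of the end of the accrual period.
- Define the information fraction as n/224.
- State which boundaries were applied at each look already taken. Compute every remaining boundary from the stated O'Brien-Fleming spending function at the actual fraction, conditional on those past boundaries.
- Remove the equal-spacing and one-third wording from the current plan.
- Label the three-analysis sentence in IV.D.4 as describing the original power tables (totals up to 150). Deleting it would leave those tables unexplained.

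The cost is a wording change and a short calculation at each remaining look. It needs no new data and no change in sample size.
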